### **Follow-up visits**

Patients enrolled in the study will be called for supportive periodontal therapy considering their SPT program and supragingival debridement will be performed accordingly to their group (control or test). All clinical variables will be re-examined by the same blinded examiner ([name]) after the first SPT visit, at 1 year and 2

## **SPECIFIC COMMISSION OF THE DOCTORAND**

years of follow-up. Additionally, a periapical radiograph of all implants involved in the study will be taken at 1 year and 2 years of follow-up. Individual compliance will be registered as well in the CRF.

Patients will be further motivated with respect to oral hygiene habits during the entire period of the study.

### *2.5 Clinical and VAS examination*

A guidebook will be prepared to standardize procedures throughout the protocol, step by step, for all questionnaires and evidence collection. The data will be transferred to a computerized database.

The study variables will be recorded in a case report form (CRF) specially designed for the study. Each study patient will be assigned a numerical code comprising a 3-digit patient code (assigned correlatively as they are included in the study). Only the study investigator will be able to identify the patient by their code.

### **Anthropometric and socio-demographic data**

An initial questionnaire will be conducted to obtain information regarding age, race, gender, medical history, medication, and health behavior (smoking habits). Smoking behavior will be specified as 3 categories: never smoker, former smoker, or current smoker (light smokers: < 10 cigarettes/day). Patients will be asked about their tobacco smoke exposure in terms of consumption (i.e. the number of cigarettes consumed per day); duration (i.e. the number of years of smoking); and lifetime exposure (i.e. the accumulated exposure as formed by the product of consumption and duration: cigarette-years). In case of former smokers, patients will be asked about the smoke-free time following cessation.

### **Clinical Parameters**

The following clinical parameters will be evaluated by the same examiner ([name]) using a manual periodontal probe PCP-UNC 15 (HuFriedy®, [name]):

1. Full mouth plaque index (FMPI) will be assessed dichotomously at four sites per tooth (mesial, buccal, distal and lingual). Presence or absence will be recorded after staining with an erythrosine disclosing dye (Plac-Control®, Dentaïd SL, Cerdanyola, Spain). Presence of plaque will be scored if an area of clearly stained material is present along the gingival margin and if this material can be removed with the side of the probe. The percentage of surfaces with plaque out of the total number of examined tooth surfaces will be calculated (O'Leary et al., 1972).
2. Full mouth bleeding index (FMBI) will be assessed dichotomously as presence or absence of bleeding after 30 seconds of gently probing. The proportion of bleeding surfaces out of the total number of examined surfaces will be calculated (Ainamo and Bay, 1975).
3. Full mouth PPD measured at six aspects around tooth.
4. Gingival Recession (GR) will be recorded at six aspects per implant: mb, b, db, ml, l and dl.
5. mPI (Mombelli et al., 1987) will be measured at six aspects around implants:

## SPECIFIC COMMISSION OF THE DOCTORAND

Score 0 - no detection of plaque.

Score 1 - plaque only recognized by running a probe across the smooth marginal surface of the implant.

Score 2 - plaque can be seen by the naked eye.

Score 3 - abundance of soft matter.

6. mBI (Mombelli et al., 1987) will be assessed 30 seconds after 0.15 N force probing.

Score 0 - no bleeding.

Score 1 - isolated bleeding spots visible.

Score 2 - blood forms a confluent red line on margin.

Score 3 - heavy or profuse bleeding. This variable will be dichotomized in presence/absence of bleeding and will serve as the main variable.

7. SOP evaluated after assessing dichotomously the presence of suppuration within 30 seconds after gentle probing.
8. Implant PPD, measured from the mucosal margin to the bottom of the probable pocket, determined at six aspects per implant: mb, b, db, ml, l and dl with a resin splint.
9. MR at the implant will be recorded at six aspects per implant: mb, b, db, ml, l and dl.

### ***Outcomes of the study***

#### **Main outcome;**

- Patient Pain/Discomfort (VAS) reported after decontamination during SPT.

#### **Secondary outcome;**

- *Changes in the following clinical variables: FMPI, FMBI, PPD, GR, mPI, mBI, SOP, Implants PPD and MR after decontamination during SPT.*
- Compliance to SPT reported after decontamination during SPT.

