### ***Sample Size Calculation***

The sample size will be calculated using changes in CAL as the primary outcome variable. Thirty patients (15 subjects in each group) were necessary to detect a difference of  $\geq 1$  mm in CAL assuming a mean standard deviation (SD) of 0.9. This calculation assumes an alpha error of 0.05, a beta error of 0.2, and a statistical power of 80%. In addition, 12% of loss to follow-up was considered.

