### **Screening examination**

The clinician will review with the patient the Information and Medication History Forms and record the anthropometric, socio-demographic and clinical information. Candidates will undergo an oral pathology examination and a full-mouth manual probing using a periodontal probe PCP-UNC 15 (HuFriedy®, [name]) to determine their periodontal and peri-implant status. Presence or absence of plaque will be recorded after staining with an erythrosine disclosing dye (Plac-Control®, Dentaid SL, Cerdanyola, Spain). Finally, periapical radiographs (Dürr Dental AG, Bietigheim-Bissingen, Germany) of all implants will be taken using a paralleling cone technique and a film-holder (7mA- 60kV/20ms).

The same calibrated examiner ([name]) will record clinical variables of mPI, BOP, PPD, MR and clinical attachment level (CAL).

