#### *Inferential analysis*

Data will be calculated at patient level and implant/tooth level. VAS score will be considered as the main outcome (quantitative).

If the distribution is normal, the following tests will be used:

- Binary categorical variables: T-Student / Fisher's exact test;
- Categorical variables with > 2 categories: ANOVA;
- Quantitative variables: Simple linear regression / Pearson correlation coefficient.

If it doesn't follow normality:

- Binary categorical variables: U of Mann-Whitney;
- Categorical variables > 2 categories: H of Kruskal-Wallis;
- Quantitative variables: Spearman's correlation coefficient.

[figure not shown]

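### Baseline values of the secondary clinical outcomes are recorded but enter no planned analysis; adjusting for them costs almost nothing and gains precision unless the baseline/follow-up correlation is high

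*Combined protocol and SAP*

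**What the plan says.** Under Outcomes of the study, the secondary clinical outcomes are "Changes in the following clinical variables: FMPI, FMBI, PPD, GR, mPI, mBI, SOP, Implants PPD and MR after decontamination during SPT".

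Baseline data exist. In the Screening examination, which precedes randomization, the calibrated examiner "will record clinical variables of mPI, BOP, PPD, MR and clinical attachment level (CAL"). Stained plaque and full-mouth probing are also recorded there. For listed outcomes not named at screening, such as GR and SOP, a baseline is implied because the outcome is a change and because the Follow-up visits section says "All clinical variables will be re-examined by the same blinded examiner". Those assessments fall after the first SPT visit, at 1 year and at 2 years.

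The Inferential analysis section opens with VAS as the main outcome and then lists tests by type of variable. For normal data it gives "Binary categorical variables: T-Student / Fisher's exact test", ANOVA, and "Quantitative variables: Simple linear regression / Pearson correlation coefficient". For non-normal data it gives "Binary categorical variables: U of Mann-Whitney", Kruskal-Wallis and Spearman. No ANCOVA, multivariable model, mixed model or baseline covariate appears in the document. Randomization uses permuted blocks of four, with no stratification described.

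The Sample Size Calculation states: "The sample size will be calculated using changes in CAL as the primary outcome variable".

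**The concern.** Every method listed relates the outcome to one factor. The regression named has a single predictor, so it cannot hold both arm and baseline. If these tests are applied to the changes, the baseline is only subtracted. Subtraction fixes its coefficient at 1, whereas the best coefficient is the regression slope, which is below 1 when variances are equal and the correlation is imperfect.

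Two things follow. The arm difference is estimated less precisely than the same data allow, and an arm that starts worse by chance tends to improve more through regression to the mean. Blocks of four balance numbers, not baseline clinical status, and the arms are small. Specific hypothesis 2 expects clinical outcomes not to differ between methods, so the width and position of the interval determine what can be said.

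**Working it through.** **Inputs.** From the Sample Size Calculation: difference 1 mm in change in CAL, SD 0.9, alpha 0.05, power 80%, 12% loss, 15 per group. Assumptions: two-sided alpha (it reproduces the stated N); 0.9 is the SD of change; equal variances at baseline and follow-up; baseline/follow-up correlation rho, which the documents do not give, ranged from 0.3 to 0.9. CAL is used only because it is the one clinical variable with an SD; it is not among the listed secondary outcomes.

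**1. The plan's figure.** n per arm = 2 × 0.9² × (1.960 + 0.842)² / 1² = 12.7, so 13. Then 13 / 0.88 = 14.8, so 15 per arm and 30 in total. This matches.

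**2. Power of the change score.** With 13 evaluable per arm, the standard error is 0.9 × √(2/13) = 0.353 mm and the noncentrality is 1 / 0.353 = 2.83 on 24 df. Power is 77.6% by noncentral t (80.9% by the normal formula).

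**3. Adjusted analysis.** With single-visit variance σ², Var(change) = 2σ²(1 − rho) and the ANCOVA residual variance is σ²(1 − rho²). The ratio is (1 + rho)/2. Estimating the slope inflates the variance by about 1 + 1/(2n − 4) = 1 + 1/22 = 1.045 and costs one degree of freedom, leaving 23.

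**4. Shift from imbalance.** Given a baseline difference D between arms, the change-score contrast moves by (1 − rho)D in the opposite direction. One SD of D is σ√(2/13), with σ = 0.9/√(2(1 − rho)).

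| rho (assumed) | Variance ratio | Ratio net of slope cost | Adjusted power | Change-score shift per 1-SD imbalance |
|---|---|---|---|---|
| 0.3 | 0.65 | 0.68 | 90.8% | 0.21 mm |
| 0.5 | 0.75 | 0.78 | 86.5% | 0.18 mm |
| 0.7 | 0.85 | 0.89 | 82.1% | 0.14 mm |
| 0.8 | 0.90 | 0.94 | 79.9% | 0.11 mm |
| 0.9 | 0.95 | 0.99 | 77.7% | 0.08 mm |

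The comparison is with 77.6% for the change score. The approximate 95% CI half-width is 2.064 × 0.353 = 0.73 mm for the change score, against about 0.60, 0.65 and 0.69 mm adjusted at rho 0.3, 0.5 and 0.7.

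**5. Simulation check.** With 20,000 replicates at 13 per arm, adjusted power was 90.8%, 86.4%, 82.2% and 77.4% at rho 0.3, 0.5, 0.7 and 0.9; unadjusted power was 77% to 78%. The correlation between the estimate and the baseline imbalance was −0.60, −0.50, −0.39 and −0.23 for the change score and about 0 for ANCOVA.

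**6. How likely is an imbalance?** P(standardized difference above 0.5 in either direction) = 2 × (1 − Φ(0.5/√(2/n))), which is 17% at n = 15 and 20% at n = 13.

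**7. Break-even.** (1 + rho)/2 × 23/22 = 1 gives rho = 0.913. Above that, adjustment is marginally less precise, by at most the 4.5% slope cost.

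**The case against.** The strongest reply has four parts.

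- **The analysis is unspecified rather than wrong.** The test list is built around VAS and never assigns a test to the change variables. A reader might infer that the plan commits to raw-change t-tests; the documents do not say so. This stands. But no other analysis is given for these outcomes, so either way the baseline has no stated use as a covariate.
- **A change-score comparison is sound.** A reader might infer that it is biased. Under randomization it is not, and its standard error already allows for chance imbalance. This stands too. The shift is conditional on the imbalance that actually occurs, which still matters when interpreting one trial of 30 patients.
- **The size is borrowed and may be nil.** CAL is not a listed secondary outcome, and no listed outcome has an SD. A reader might infer a gain whenever rho is below 1. That is a large-sample statement; with 26 completers the gain has gone by rho of about 0.9. Both limits stand, so the figures illustrate and do not measure the effect on the listed outcomes.
- **A narrower interval does not establish sameness.** Hypothesis 2 has no stated margin, and baseline adjustment does not supply one. This stands; adjustment only improves the interval that any such judgement would use.

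None of this removes the omission.

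**Conclusion.** The point holds as an avoidable loss of precision and of protection against chance imbalance in the secondary clinical outcomes. It is not an invalid analysis. In the CAL illustration, the net variance reduction is about 32%, 22% and 11% at rho 0.3, 0.5 and 0.7, 6% at 0.8, and essentially none at 0.9. This rests on an assumed rho, equal variances, 0.9 being the SD of change, and 13 evaluable patients per arm.

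A reader might extend the point to the main outcome. The documents do not support that: VAS is taken after debridement, and no pre-treatment VAS is described. Nor does the point call for a different sample size.

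**What to change.** In the Inferential analysis section, add the following.

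- **Quantitative variables** (FMPI, FMBI, PPD, GR, implant PPD, MR and patient-mean mPI): at each follow-up assessment (after the first SPT visit, 1 year, 2 years), compare arms by ANCOVA of the follow-up value on arm plus baseline at patient level. For implant- or tooth-level data, use a mixed model with the same terms, clustered on patient.
- **Dichotomized mBI and SOP:** use a baseline-adjusted binary or site-proportion model, clustered on patient.
- **Reporting:** give adjusted differences with 95% CIs, and keep the unadjusted tests as supporting analyses.

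The Screening examination section should also confirm that every listed outcome, including GR and SOP, is recorded before randomization.

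The cost is a few sentences of text. No extra patients are needed, and no new data if the implied baselines are recorded.

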### ***Intra-examiner reproducibility***

Reproducibility of clinical examinations will be conducted by the examiner ([name]), evaluating the Implant PPD and mBI in 5 patients, not involved in the study, on two separate occasions, 1 week apart. The intra-class correlation coefficient and the kappa index will be calculated. Calibration will be accepted when

## **SPECIFIC COMMISSION OF THE DOCTORAND**

measurements at baseline and at one-week evaluation will be within a difference of 0.5 mm >90% of the time.

### ***Withdrawal of consent***

The Patient Information Sheet will clearly state that the patient can withdraw from the study at any time without prejudice or explanation. Such withdrawal will be documented in the medical record file. Losses to follow-up are taken into account in the sample size calculations (12%).

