#### b) Specific Hypothesis

1. SPT with conventional ultrasonic device will result in more pain/discomfort around dental implants than in teeth.
2. SPT by means of an erythritol based air-polishing powder (Air Flow Master®, Air-Flow Plus®, EMS, Nyon, Switzerland) will result in better patient reported outcomes and same clinical outcomes, at the first SPT and after 2 years.
3. SPT by means of an erythritol based air-polishing powder (Air Flow Master®, Air-Flow Plus®, EMS, Nyon, Switzerland) will result in the increase of the compliance rates after 2 year of follow-up.

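### The 1- and 2-year clinical outcomes are at risk of selection bias: re-examination is organised around SPT recalls, the device is expected to change attendance, and losses are met only by a 12% allowance.

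*Combined protocol and SAP*

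**What the plan says.** **Follow-up.** Under Follow-up visits, "Patients enrolled in the study will be called for supportive periodontal therapy considering their SPT program". The clinical variables are then re-examined after the first SPT visit and at 1 and 2 years. No study visit separate from SPT is described, and no procedure is given for examining patients who stop attending.

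**Expected effect on attendance.** Specific Hypothesis 3 says that air-polishing "will result in the increase of the compliance rates after 2 year of follow-up". Compliance is also a secondary outcome. Specific Hypothesis 2 expects clinical outcomes to be the same in both arms at the first visit and at 2 years.

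**Attendance classes.** Under Compliance Definition, regular compliers have at least two SPT visits a year, erratic compliers are on a 7- to 12-month interval, and non-compliers have none in the year.

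**Losses.** Under Withdrawal of consent, "Losses to follow-up are taken into account in the sample size calculations (12" per cent). Sample Size Calculation applies the same overall figure and does not split it by arm.

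**Analysis.** The Statistical analysis section lists univariable tests chosen by variable type and normality. It states no analysis population, as-randomised principle, missing-data method or sensitivity analysis.

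**The concern.** Three statements in the protocol form a chain. The device is expected to change attendance. Attendance is the only described route to the later examinations. The background section on compliance also names absence of regular maintenance as making peri-implant disease more likely, and reports that smoking and periodontal history go with compliance. Whether a patient has 2-year data may therefore depend on both treatment and prognosis.

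The listed tests, run without further rules, use whoever was examined. If more of the less motivated or more diseased patients stay in the test arm than in the control arm, the examined groups are no longer comparable. The conclusion most exposed is that of equal clinical outcomes at 2 years. Selective loss can hide a real difference or create a false one, and a larger sample removes neither. Classing discontinuers as erratic or non-compliers completes the compliance endpoint but supplies no 2-year probing depth, bleeding or suppuration value.

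**Working it through.** **1. The plan's own figure.** The inputs come from Sample Size Calculation: a 1 mm difference in clinical attachment level (CAL), SD 0.9, alpha 0.05 (two-sided assumed, as the plan does not say) and power 80%.

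- n per arm = 2 × (0.9 × (1.960 + 0.842) / 1)² = 12.7, rounded up to 13.
- With 12% loss: 13 / 0.88 = 14.8, rounded up to 15 per arm, 30 in total.

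This reproduces "Thirty patients (15 subjects in each group) were necessary to detect a difference of" 1 mm. The allowance is correct for precision. CAL is used below only as a scale for the SD; the main outcome is VAS.

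**2. A false difference when there is none.** The documents give no attendance rate by arm and no strength for the link with outcome, so both are assumed. Severity is standard normal in both arms, with no device effect on it. The log-odds of being examined fall by 1 per SD of worse severity: P(seen) = 1 / (1 + exp(−(a − severity))), with a chosen to give the stated share seen. The spurious difference is the mean severity among test patients seen minus that among control patients seen.

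| Seen, control v test | Overall loss | Mean among seen, control / test (SD) | Spurious difference | × 0.9 mm |
|---|---|---|---|---|
| 88% v 88% | 12% | −0.11 / −0.11 | 0 | 0 |
| 82% v 94% | 12% | −0.16 / −0.06 | 0.10 SD | 0.09 mm |
| 76% v about 100% | 12% | −0.21 / 0.00 | 0.20 SD | 0.18 mm |
| 60% v 90% | 25% | −0.33 / −0.09 | 0.24 SD | 0.22 mm |

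In each unequal row the better-attended arm looks worse.

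**3. A second model as a cross-check.** Suppose some patients attend only because of the device, and their outcome is worse by D than in those who would attend anyway. Then bias = D × (pT − pC) / pT, where pT and pC are the shares seen in test and control. With D assumed at 0.45 to 0.9 mm and 15 randomised per arm:

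- 94% v 82%: 0.45 × 0.12 / 0.94 = 0.06 mm, to 0.9 × 0.12 / 0.94 = 0.11 mm. False-positive rate 5.3% to 6.2%.
- 100% v 76%: 0.11 to 0.22 mm. False-positive rate 6.1% to 9.4%.
- 90% v 60%: 0.15 to 0.30 mm. False-positive rate 6.7% to 12.1%.

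The bias is zero if D = 0, if attendance is equal, or if everyone is examined.

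**4. A real difference hidden.** Suppose instead that non-attenders end 1 SD worse (assumed) and attenders are alike in the two arms. The true difference among all randomised is (pT − pC) × 1 SD, while those examined show 0. That is 0.12 SD at 94% v 82%, 0.24 SD at 100% v 76%, and 0.30 SD at 90% v 60%.

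**5. Change scores.** The secondary clinical outcomes are defined as changes. If attendance depends on baseline severity and the baseline-to-follow-up correlation is r, the bias in change is −(1 − r) times the figure in step 2. At 60% v 90% this is 0.3 × 0.24 = 0.07 SD for r = 0.7, or 0.5 × 0.24 = 0.12 SD for r = 0.5, with the sign reversed.

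**The case against.** The strongest reply is that most of this is read from silence. Nothing says that only available patients will be compared. Follow-up visits sets re-examination at fixed times and does not limit it to compliers. This stands: the plan permits the problem but does not prescribe it.

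A reader might infer that, if Hypothesis 3 is true, missing data must differ between the arms. The documents do not support that. Erratic compliers can still be seen about once a year, so compliance could rise through a shift from erratic to regular attendance with no change in who has an annual examination. The patients likely to lack data are mainly the non-compliers, and no rate is given for them.

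A reader might also infer that the main outcome is compromised. At the first SPT visit, randomisation, debridement and the VAS follow one another, so later attendance cannot affect that score. Only a later VAS is exposed, and an examination without debridement could not recover it.

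On size, 60% v 90% means about twice the loss the protocol allows for, so it should not be the headline. At the protocol's own 12%, the bias is modest beside a 1 mm design difference. That difference was set for detecting an effect, however; the plan gives no margin for calling clinical outcomes the same, so a small bias cannot be dismissed on that ground.

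**Conclusion.** The concern holds as a risk of bias in the 1- and 2-year clinical comparisons, not as a demonstrated bias. It needs two things: an attendance difference large enough to change who is examined, and a link between attendance and outcome. The protocol's hypothesis and background make both plausible, but neither can be quantified from the documents.

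Under the assumed attendance model and no true effect, the spurious difference is about 0.10 to 0.20 SD at the planned 12% overall loss, and 0.24 SD at 25% loss with 60% v 90% seen. For change scores the size may be smaller and the direction opposite, so the sign cannot be predicted. First-visit VAS is not affected, and compliance is affected little if it is counted from visit records for all randomised patients. The 12% allowance is correctly calculated but does not address this risk.

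**What to change.** **Follow-up visits.** State that every randomised patient is invited to the 1- and 2-year study examinations whether or not SPT recalls were kept, and that this examination does not count as SPT attendance.

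**Inferential analysis.** Analyse all randomised patients as allocated. For the continuous clinical outcomes, use a baseline-adjusted repeated-measures model on all visits (arm, visit, arm-by-visit). For mBI, SOP and mPI, use a suitable binary or ordinal version, kept simple given about 30 patients. Report missingness by arm and visit. Because such a model does not cover loss that depends on unobserved values, add a sensitivity analysis with missing 2-year values set worse, for example by 0.5 to 1 SD for continuous outcomes.

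**VAS.** Label any 2-year VAS as conditional on attending for debridement.

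**Cost.** Recall calls for examinations already planned, a few sentences of text and slightly more analysis. Contacting non-attenders may nudge attendance in both arms, which is a small price because values never collected cannot be recovered at analysis.
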